#### 6.5.1.2 Tumor Response on CT (RECIST)

Measurable Disease Response: CTEP's RECIST guidelines will be followed. A quick reference to the RECIST guidelines can be downloaded at the following URL: http://ctep.info.nih.gov/Policies/WordDocs/RCSTF.PH2TEMPF.doc. (Appendix II) Patients enrolled in this study must have a measurable liver metastasis which is defined as lesions that can be accurately measured in at least one dimension: [longest diameter to be recorded] on the CT scan.

The same method of assessment and the same technique should be used to characterize each identified & reported lesion at baseline & during follow-up.

F	Parameters to Measure Response Outcome:			
1 Clinical examination				
2	CT scan			
3	FDG-PET/CT scan			

Taking into account the measurement of the longest diameter only for those lesions with size response, response criteria are defined as:

- 1. Complete Response (CR): the disappearance of a lesion.
- 2. Near Complete Response (NCR): at least an 80% decrease in the longest diameter of a lesion, taking as reference the longest diameter recorded since the treatment started.
- 3. Partial Response (PR): at least a 30% decrease in the longest diameter of a lesion, taking as reference the longest diameter recorded since the treatment started.
- 4. Progressive Disease (PD): at least a 25% increase in the longest diameter of a lesion, taking as reference the longest diameter recorded since the treatment started.
- 5. Stable Disease (SD): neither sufficient shrinkage to qualify for partial response nor sufficient increase to qualify for progressive disease, taking as reference the longest diameter since the treatment started.

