## 6.5.1.3 Tumor Response on F-FDG-PET/CT

The most recent consensus recommendations by the NCI on assessing PET response indicate semiquantitative SUV (standard uptake value) analysis based on lean body mass and/or body surface area be used in determining F-FDG uptake. The SUV is calculated using the tumor radiotracer concentration (Q [MBq/l]), body surface area (BSA [m²] and injected activity (Qinj [MBq]):

$$SUV_{BSA} = (Q \times BSA)/Q_{ini}$$

The subject's body surface area is calculated using weight (W [kg]) and height (H [cm]):

$$BSA = W^{0.425} \times H^{0.725} \times 0.00718$$

We will use the EORTC 1999 criteria for defining F-FDG response.

- 1. Progressive Metabolic Disease (PMD): An increase in F-FDG tumor SUV of greater than 25% within the tumor region defined on baseline scan, visible increase in the extent of F-FDG tumor uptake (> 20% in the longest dimension) or the appearance of new F-FDG uptake in metastatic lesions.
- 2. Stable Metabolic Disease (SMD): An increase in tumor SUV of < 25% or a decrease < 15% and no visible increase in extent of F-FDG tumor uptake (> 20% in the longest dimension).
- 3. Partial Metabolic Response (PMR): A reduction of a minimum of 25% in tumor F-FDG SUV uptake. A reduction in the extent of tumor F-FDG is not required to be classified as a PMR.
- 4. Complete Metabolic Response (CMR): Complete resolution of F-FDG uptake within the tumor volume so that it is indistinguishable from surrounding normal tissue.

For those patients with non-FDG avid tumors, their response to therapy will be assessed by CT scan as detailed in 6.5.1.2.

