#### 6.5.1.5 Definition of local control

Local control will be defined as sustained stable disease, partial response, or complete response in the target lesion(s) at one year post-treatment.

Local Response Rate is defined as stable disease, partial response, or complete response per RECIST at any point in the first year of follow-up.

Local failure will be defined as any progression of disease within the target volume.

Regional failure will be defined as development of new liver metastases outside of the treated lesions.

Distant failure will be defined as development of new metastatic lesions outside of the liver (brain, bone, etc).

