#### Response Criteria

## **Evaluation of target lesions**

* Complete Response (CR):	Disappearance of all target lesions
* Partial Response (PR):	At least a 30% decrease in the sum of the LD of target lesions, taking as reference the baseline sum LD
* Progressive Disease (PD):	At least a 20% increase in the sum of the LD of target lesions, taking as reference the smallest sum LD recorded since the treatment started or the appearance of one or more new lesions
* Stable Disease (SD):	Neither sufficient shrinkage to qualify for PR nor sufficient increase to qualify for PD, taking as reference the smallest sum LD since the treatment started
	Evaluation of non-target lesions

* Complete Response	Disappearance of all non-target lesions and normalization of tumor				
(CR):	marker level				
* Incomplete	Persistence of one or more non-target lesion(s) or/and maintenance of				
Response/	tumor marker level above the normal limits				
Stable Disease (SD):					
* Progressive Disease	Appearance of one or more new lesions and/or unequivocal				
(PD): progression of existing non-target lesions (1)					

(1) Although a clear progression of "non target" lesions only is exceptional, in such circumstances, the opinion of the treating physician should prevail and the progression status should be confirmed later on by the review panel (or study chair).

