#### **Evaluation of best overall response**

The best overall response is the best response recorded from the start of the treatment until disease progression/recurrence (taking as reference for PD the smallest measurements recorded since the treatment started). In general, the patient's best response assignment will depend on the achievement of both measurement and confirmation criteria

Target lesions	Target lesions Non-Target lesions		Overall response
CR	CR	No	CR
CR	Incomplete	No	PR
	response/SD		
PR	Non-PD	No	PR
SD	Non-PD	No	SD
PD	Any	Yes or No	PD
Any	PD	Yes or No	PD
Any	Any	Yes	PD

- Patients with a global deterioration of health status requiring discontinuation of treatment without objective evidence of disease progression at that time should be classified as having "symptomatic deterioration". Every effort should be made to document the objective progression even after discontinuation of treatment.
- In some circumstances it may be difficult to distinguish residual disease from normal tissue. When the evaluation of complete response depends on this determination, it is recommended that the residual lesion be investigated (fine needle aspirate/biopsy) to confirm the complete response status.

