#### **Duration of stable disease**

- SD is measured from the start of the treatment until the criteria for disease progression are met, taking as reference the smallest measurements recorded since the treatment started.
- The clinical relevance of the duration of SD varies for different tumor types and grades. Therefore, it is highly recommended that the protocol specify the minimal time interval required between two measurements for determination of SD. This time interval should take into account the expected clinical benefit that such a status may bring to the population under study.

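### CT progression has two unreconciled definitions (section 6.5.1.2 and Appendix II), so the same scans can count as local control or as progression

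*Combined protocol and SAP*

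**What the plan says.** Section 6.5.1.2 (Tumor Response on CT) opens with "CTEP's RECIST guidelines will be followed" and refers to Appendix II. It then gives its own list of categories, each for a single lesion. Progressive disease is "at least a 25% increase in the longest diameter of a lesion, taking as reference the longest diameter recorded since the treatment started".

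The definition of progressive disease in Appendix II (Evaluation of target lesions) reads, in part, "At least a 20% increase in the sum of the LD of target lesions, taking as reference the smallest sum LD recorded since"; the count runs from the beginning of therapy, and any new lesion is progression as well. The smallest-value reference recurs under Evaluation of best overall response, "taking as reference for PD the smallest measurements recorded since the treatment started", in the same terms under Duration of overall response, and under Duration of stable disease, "taking as reference the smallest measurements recorded since the treatment started".

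Section 6.5.1.5 states: "Local control will be defined as sustained stable disease, partial response, or complete response in the target lesion(s) at one year post-treatment". It names no criteria set for local control, cites RECIST only for the local response rate, and defines local failure as any progression in the target volume without a threshold. For tumours that are not FDG-avid, section 6.5.1.3 says "their response to therapy will be assessed by CT scan as detailed in 6.5.1.2". Section 7.3.2 tabulates local control and local failure with exact 95% confidence intervals.

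**The concern.** The two definitions differ in threshold (25% against 20%), unit (one lesion against the sum) and reference (longest against smallest). The plan sends readers to both: section 6.5.1.3 to section 6.5.1.2 for some patients, and section 6.5.1.5 to RECIST for local response. It leaves local control and local failure unassigned.

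The reference matters most. A lesion that shrinks and then regrows is a local failure that a sustained-control endpoint at one year should detect. Measured against the longest diameter, that regrowth is called late or never.

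The phrase in section 6.5.1.2 is also unclear in itself. It could mean the pre-treatment diameter, the running maximum, or the largest post-treatment value. At stake is secondary objective 2.2: the reported rate would not show which rule produced it.

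**Working it through.** The plan gives no figure to reproduce, so both rules are applied to the same diameters. The diameters are assumed for illustration. Section 4.3 allows up to three lesions of at most 3 cm each, or one of at most 6 cm, so 30 mm is the largest size permitted when there are several lesions. The scan times (months 2, 5, 8 and 11) are from section 6.6. The maximum of 18 evaluable patients is from section 7.2, and up to 6 per dose level from section 7.1.

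**Single lesion, 30 mm before treatment.** Appendix II calls progression at 1.2 × smallest diameter. Section 6.5.1.2 with the pre-treatment reference calls it at 1.25 × 30 = 37.5 mm, whatever the smallest diameter.

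| Smallest diameter (mm) | Appendix II (mm) | Section 6.5.1.2 (mm) |
|---|---|---|
| 30 | 36.0 | 37.5 |
| 27 | 32.4 | 37.5 |
| 21 | 25.2 | 37.5 |
| 15 | 18.0 | 37.5 |

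After a fractional shrinkage s, the regrowth from the smallest size needed under section 6.5.1.2 is 1.25/(1 − s) − 1. That is 78.6% for s = 0.30 and 150% for s = 0.50, against 20% under Appendix II.

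Example, 30 → 15 → 24 mm: 24/30 − 1 = −20%, stable under section 6.5.1.2; 24/15 − 1 = +60%, progression under Appendix II.

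**Readings of the section 6.5.1.2 reference.**
- Running maximum, 30 → 33 → 40 mm: the threshold is 1.25 × 33 = 41.25 mm, so 40 mm (40/33 = +21.2%) is not progression. On the pre-treatment reading (40/30 = +33.3%) and under Appendix II it is.
- Running maximum, slow growth 30 → 36 → 44 → 54 → 66 mm: the steps are +20.0%, +22.2%, +22.7% and +22.2%. None reaches 25%, although 66/30 = +120%. Over four scans the limit is just under 1.25⁴ = 2.44 times baseline.
- Pre-treatment value excluded, first scan 15 mm: 1.25 × 15 = 18.75 mm against 18.0 mm, almost no difference.

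**Several lesions.** Take k lesions of 30 mm. One has smallest diameter n and the others stay at 30 mm. Appendix II calls progression when the changing lesion reaches 1.2 × (30(k − 1) + n) − 30(k − 1) mm:
- k = 2: 6 + 1.2n, equal to 37.5 mm at n = 26.25 mm.
- k = 3: 12 + 1.2n, equal to 37.5 mm at n = 21.25 mm.

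Appendix II is therefore the earlier rule only if n is below 26.25 mm (two lesions) or 21.25 mm (three). With three lesions and no shrinkage it needs 12 + 36 = 48.0 mm, against 37.5 mm.

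**Effect on the rate (exact 95% intervals).** One patient is 1/18 = 5.6 points overall, or 1/6 = 16.7 points in a dose group of six.
- 17/18 = 94.4% (72.7 to 99.9); 16/18 = 88.9% (65.3 to 98.6).
- 6/6 = 100% (54.1 to 100); 5/6 = 83.3% (35.9 to 99.6).

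**Local response rate.** For a single lesion this is little affected: at the first follow-up scan a 30 mm lesion is called progressed at 36.0 or 37.5 mm.

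**The case against.** The best defence is that section 6.5.1.2 is the study-specific text and Appendix II a generic quick reference, so the body should govern. A per-lesion rule also suits a local endpoint. This is a reasonable guess at intent, but the same section says RECIST is followed, and nothing states precedence or a deliberate departure.

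Second, longest diameter may simply name the measurement, as it does elsewhere in section 6.5.1.2. The reference time is then unstated. If it is the smallest value, a single lesion differs only in the 20 to 25% band. That would shrink the problem but not remove it: 40 → 20 → 24.5 mm is 24.5/20 − 1 = +22.5%, progression under Appendix II only. Lesion against sum also stays open.

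Third, the slow-growth series is extreme, and a reader might call it local failure anyway, since section 6.5.1.5 counts any progression. Section 6.3.3 can also be read as allowing a fifth scan. The series shows the ambiguity, not a likely outcome.

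Fourth, the new-lesion clause matters little for local control, because section 6.5.1.5 assigns new lesions to regional or distant failure. That stands.

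Finally, the impact is modest. The endpoint is secondary, section 7.3 calls the analysis exploratory, no test or threshold applies to local control, and the intervals above overlap widely. That limits the seriousness of the point but does not settle which rule applies.

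**Conclusion.** The concern holds. The plan has two progression rules for CT, both in force and not reconciled, and they can classify one patient's scans in opposite ways. Read literally, the longest-diameter reference misses regrowth after shrinkage. For a single lesion on the pre-treatment or running-maximum reading, this favours local control. With two or three lesions Appendix II can be the more lenient, so no net direction can be derived.

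The number of patients affected is unknown. The point shifts per patient assume all 18 evaluable patients, or 6 in a dose group, as denominator. Confidence is high in the mismatch and lower in its practical effect. The maximum tolerated dose and the escalation decisions are untouched. It should be corrected, but it does not threaten the primary objective.

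**What to change.** State one progression rule for treated lesions in section 6.5.1.2, without the longest-diameter reference, and say whether any difference from Appendix II is intended. One suitable rule, close to the standard the protocol cites, is an increase of at least 20% over the smallest diameter since treatment started, counting baseline, with partial and near complete response measured from baseline.

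State also whether the rule applies per lesion or to the sum. Per lesion departs from Appendix II and is stricter with several lesions. Take three 30 mm lesions, one going 30 → 15 → 18 mm. The per-lesion 20% rule gives progression (18/15 = +20%), whereas section 6.5.1.2, with the pre-treatment or running-maximum reference, gives partial response (18/30 = −40%) and the Appendix II sum goes from 75 to 78 mm (+4%). In section 6.5.1.5, tie local control, local response and local failure to the chosen rule.

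The cost is wording only, with the same scans and measurements. The local control rate may come out lower, particularly under a per-lesion rule, or higher if the sum rule is chosen, by 5.6 points out of 18 for each patient reclassified.

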## 6.5.1.3 Tumor Response on F-FDG-PET/CT

The most recent consensus recommendations by the NCI on assessing PET response indicate semiquantitative SUV (standard uptake value) analysis based on lean body mass and/or body surface area be used in determining F-FDG uptake. The SUV is calculated using the tumor radiotracer concentration (Q [MBq/l]), body surface area (BSA [m²] and injected activity (Qinj [MBq]):

$$SUV_{BSA} = (Q \times BSA)/Q_{ini}$$

The subject's body surface area is calculated using weight (W [kg]) and height (H [cm]):

$$BSA = W^{0.425} \times H^{0.725} \times 0.00718$$

We will use the EORTC 1999 criteria for defining F-FDG response.

- 1. Progressive Metabolic Disease (PMD): An increase in F-FDG tumor SUV of greater than 25% within the tumor region defined on baseline scan, visible increase in the extent of F-FDG tumor uptake (> 20% in the longest dimension) or the appearance of new F-FDG uptake in metastatic lesions.
- 2. Stable Metabolic Disease (SMD): An increase in tumor SUV of < 25% or a decrease < 15% and no visible increase in extent of F-FDG tumor uptake (> 20% in the longest dimension).
- 3. Partial Metabolic Response (PMR): A reduction of a minimum of 25% in tumor F-FDG SUV uptake. A reduction in the extent of tumor F-FDG is not required to be classified as a PMR.
- 4. Complete Metabolic Response (CMR): Complete resolution of F-FDG uptake within the tumor volume so that it is indistinguishable from surrounding normal tissue.

For those patients with non-FDG avid tumors, their response to therapy will be assessed by CT scan as detailed in 6.5.1.2.

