## Secondary

- 2.2 To evaluate the local control associated with this local regional therapy.
- 2.3 To determine local response based on FDG-PET/CT compared to CT only.
- 2.4 To evaluate the HRQL associated with this therapy

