#### 6.4 Study procedures

#### 6.4.1 PET/CT Imaging

Patients will be required to fast for at least 4 to 6 hours prior to the FDG-PET/CT imaging procedure. Prior to injection of [F]-fluorodeoxyglucose ([F]-FDG), a 1 ml blood sample (1/3 teaspoonful) will be taken to measure the patient's blood glucose level. After the injection of 10-15 mCi of [F]-FDG and an approximate 45 minute wait allowing for tracer incorporation, a CT scan will be performed for attenuation correction and anatomical correlation on the General Electric Discovery ST PET/CT (GE Medical Systems, Waukesha, WI) scanner. The CT scanner portion of the GE ST consists of a multi-detector spiral CT scanner. CT scans will be acquired as diagnostic quality CT, after the patient receives 900 ml Gastroview orally and 125 ml Optiray 350 intravenously (I.V.) through an automated injector. This will be followed by a whole body emission PET scan. The [F]-FDG is being used in this study in accordance with the current FDA regulations addressing radioactive drugs for use in PET procedures. The total scan duration, including a spiral CT scan of the same axial extent as the FDG-PET, will not exceed 60 min. A CT scan will be acquired over the same axial length as the FDG-PET scan.

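### The PET scale counts new lesions anywhere as progression and leaves SUV bands unassigned, so the PET-versus-CT comparison of local response can pick up spread outside the treated lesion

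*Combined protocol and SAP*

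**What the plan says.** Secondary objective 2.3 reads "To determine local response based on FDG-PET/CT compared to CT only". Section 7.3.2 tests it by comparing local response rates on the two modalities with McNemar's test.

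**PET (section 6.5.1.3).** PMD is met by a rise in SUV above 25%, by growth in the extent of uptake, or by new "F-FDG uptake in metastatic lesions". The new-uptake clause is not confined to the treated lesion or the liver, and section 6.4.1 describes the acquisition thus: "This will be followed by a whole body emission PET scan". Stable disease (SMD) is "An increase in tumor SUV of < 25% or a decrease < 15% and no visible increase in extent of" uptake. Partial response (PMR) is "A reduction of a minimum of 25% in tumor" SUV.

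**CT (section 6.5.1.2).** Each category is defined on the diameter of one lesion; progression, for example, is "at least a 25% increase in the longest diameter of a lesion". No category mentions new lesions. The same section also states "CTEP's RECIST guidelines will be followed" and points to Appendix II, where any new lesion is progressive disease.

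**Local endpoints (section 6.5.1.5).** Local failure is confined to the target volume. New disease is counted separately: "Regional failure will be defined as development of new liver metastases outside of the treated lesions", and new lesions outside the liver are distant failure. The local response rate is defined by RECIST at any time in the first year. No PET counterpart is given.

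**The concern.** The question is local: do the two modalities agree about the irradiated lesion? The PET scale can call a patient progressive for a reason unrelated to that lesion, and section 6.5.1.5 assigns that reason to other endpoints. McNemar's test uses only discordant pairs. If new disease elsewhere turns the PET result but not the CT result, it produces discordance in one direction (CT responder, PET non-responder) even when the modalities agree perfectly on the treated lesion.

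Separately, some SUV changes fit no PET category and some patients fit two. Without a rule written beforehand, those patients would be dropped or assigned after the data are seen, in a comparison small enough for a few patients to decide it.

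**Working it through.** **1. Apply the PET rules as printed**

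| Change in SUV of treated lesion | New lesion elsewhere | Category met |
|---|---|---|
| fall of 40% | no | PMR |
| fall of 25% | no | PMR |
| falls of 24.9%, 20%, 15% | no | none |
| fall of 14.9% | no | SMD |
| rise of 24.9% | no | SMD |
| rise of exactly 25% | no | none |
| rise of 25.1% | no | PMD |
| fall of 40% | yes | PMR and PMD |

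The main gap is 25 − 15 = 10 percentage points wide. The last row shows an overlap for which no order of precedence is given.

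**2. Follow one patient through both CT rules.** The treated lesion has disappeared on both modalities and there is a new avid lung lesion.

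- CT by section 6.5.1.2: complete response. PET: PMD by the new-lesion clause. The pair is discordant although the modalities agree on the treated lesion.
- CT by Appendix II, if the lung lesion is also seen on CT: progressive disease. PET: PMD. The pair is concordant, but a lung lesion has made the patient a local non-responder on both scales.

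Neither reading delivers objective 2.3.

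**3. Number of pairs.** Section 7.1 allows up to 6 patients at each of 3 dose levels: 6 × 3 = 18, which reproduces the maximum in section 7.2. The documents give no sample size, alpha or power for the PET-versus-CT comparison. Eighteen is a ceiling. Section 6.1.10 allows contrast CT at screening when PET is not insured, and section 6.3.3 keeps the same procedure in follow-up. Non-avid tumours are read by CT (section 6.5.1.3).

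**4. McNemar's test when all b discordant pairs lie in one direction.** Exact two-sided p = 2 × 0.5^b.

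- b = 5: 2 × 0.03125 = 0.0625
- b = 6: 2 × 0.015625 = 0.031

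Six such pairs are needed to fall below a conventional 0.05, a threshold assumed here.

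**5. Chance of six or more such pairs.** Assumptions: the modalities agree on the treated lesion, CT is read by section 6.5.1.2, PMD takes precedence and counts as non-response, and a proportion π of patients are CT responders who are PMD only through new lesions. The count is binomial (n, π), with expected value n × π. The values of π, and n = 12, are assumptions.

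| π | Expected, n = 18 | P(6 or more), n = 18 | Expected, n = 12 | P(6 or more), n = 12 |
|---|---|---|---|---|
| 10% | 1.8 | 0.6% | 1.2 | 0.1% |
| 20% | 3.6 | 13% | 2.4 | 1.9% |
| 30% | 5.4 | 47% | 3.6 | 12% |
| 40% | 7.2 | 79% | 4.8 | 34% |

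**6. Timing.** If the first-year rule for local response is carried over to PET, a patient already scored as a PET responder keeps that status when a new lesion appears later. Mainly new lesions already present at the first follow-up scan, at 8 weeks (section 6.3.3), would then turn a result. The relevant π is the proportion by about 8 weeks.

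**The case against.** The strongest reply is that the asymmetry is not settled by the text. Sections 6.5.1.2 and 6.5.1.5 both invoke RECIST, and Appendix II counts new lesions as progression. PET/CT patients also have a diagnostic-quality CT over the same axial length as the PET (section 6.4.1), so a new lesion may well count on both sides. A reader might infer that CT is unambiguously scored per treated lesion; the documents do not support that. This part stands and limits the claim of one-directional discordance. It does not rescue the comparison, because new disease elsewhere then enters both local rates.

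Second, PET local response is never defined, so it is not certain that the new-lesion clause feeds the test. A lesion-based definition would remove the problem. That is true, but the plan contains no such definition.

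Third, the unassigned 15% to 25% band lies between two non-progressive categories. Counting everything short of PMD as response, or only PMR and CMR, would settle it for the test. A reader might infer that these patients are necessarily lost; that does not follow. The plan adopts neither definition, so the gap remains a wording defect.

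Fourth, a reader might take the allowance of extra-hepatic disease at entry (section 4.3h) as evidence that new lesions will be frequent. Disease present at baseline is not new uptake, and the documents give no rate of new lesions.

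Finally, section 7.3 describes the analyses as exploratory. This bears on priority rather than on whether the rules work.

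**Conclusion.** The concern holds in a limited form. As printed, the PET scale mixes spread elsewhere into a local comparison, leaves two sets of SUV changes unclassified, and lets one patient meet two opposing categories. These findings come from the wording and need no assumption.

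The effect on McNemar's test depends on which CT rule governs, how PET local response is defined, and how many new lesions appear early. The documents fix none of these. The range of 0.1% to 79% in the working reflects that and is not a forecast. A reader might infer that a spurious significant difference is likely. That would need an early new-lesion proportion near the top of the assumed range and close to 18 usable pairs, and the documents support neither.

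The comparison is secondary and exploratory and no dose decision rests on it. This is a low-stakes correction, worth making before the data are read.

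**What to change.** For objective 2.3 only, amend sections 6.5.1.3, 6.5.1.5 and 7.3.2 as follows:

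- Score both PET and CT on the treated lesion(s), and record new lesions on either modality as regional or distant failure.
- State that the per-lesion rule of section 6.5.1.2, not the new-lesion rule of Appendix II, feeds McNemar's test.
- Name the PET categories that count as local response. CMR, PMR and SMD would mirror the CT definition.
- Assign falls of 15% to under 25%, and the rise of exactly 25%, to one category. Extending SMD to both would do it.
- Pair the same lesions at the same scan with the patient as the unit, and say how up to three lesions combine into one patient result.

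The cost is wording; no new scans or readers are needed. The downside should be stated openly: for this objective the PET scale would depart from the printed criteria in two places, the new-lesion clause and the limit of stable disease.
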